8. STUDY ASSESSMENTS AND PROCEDURES BY VISIT

8.1 Informed Consent

After the study has been fully explained, written informed consent will be obtained from either the subject or his/her guardian or legal representative prior to study participation. The method of obtaining and documenting the informed consent and the contents of the consent will comply with International Council for Harmonisation (ICH) GCP and all applicable regulatory requirement(s). Since this study will be collecting long-term follow-up assessments, the informed consent must include the expected duration of the subject's participation and the time intervals between site visits.

Logistically, the informed consent will be obtained prior to performing any study related procedures or documenting any subject data in the eCRF. If the subject does not want to commit to enrolling in the long-term follow-up study during the last visit (W96) of the RESCUE/REVERSE study, then subject may have up to 1 day prior to Visit 2 to sign the informed consent form (ICF). It will be explained and agreed to by the subject as part of the informed consent that assessment data from the RESCUE/REVERSE clinical database may be used as needed in order to complete the required data summaries and statistical analyses for the long-term follow-up study.

It will be recommended that the subject inform their primary physician about their participation in the RESCUE/REVERSE long-term follow-up study.

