8.2 Schedule of Events

The Schedule of Events (**Table 1**) provides the procedures/assessments to be performed at each scheduled visit for long-term follow-up period.

The inclusion assessments may be performed at the Week 96/EOS visit of RESCUE/REVERSE and up to 1 day prior to the Visit 2 (Year 2.5 visit [up to 180 days post Week 96]).

Table 1: Schedule of Events

Years post-treatment	Inclusion Period	Long-term Follow-up Period			
	Year 2 (Week 96) ^a	Year 2.5 (± 4 weeks)	Year 3 (± 4 weeks)	Year 4 (± 4 weeks)	Year 5 EOS (± 4 weeks) ^b
Procedure	Visit 1	Visit 2	Visit 3	Visit 4	Visit 5
Informed consent	X				
Clinical Assessments/Procedures					
Review inclusion/exclusion criteria	X				
Medical history	X				
Physical examination including vital signs ^c	X				X
Electrocardiogram (12-lead)	X				X
Review concomitant medications	X	X	X	X	X
Adverse events/serious adverse events ^d	X	X	X	X	X
Laboratory Assessments					
Hematology/serum chemistry including liver function ^e	X				X
Quality of Life Assessments					
VFQ-25 ^f	X		X	X	X
SF-36 ^f	X		X	X	X
Ocular and Vision Assessments					
Slit-lamp examination ^g	X	X	X	X	X
Goldmann applanation tonometry for intraocular pressure ^h	X	X	X	X	X
Refraction for BCVA	X	X	X	X	X
Visual Acuity (ETDRS)	X	X	X	X	X
Humphrey TM visual field 30-2	X	X	X	X	X
Pelli-Robson contrast sensitivity ^h	X		X	X	X
SD-OCT	X	X	X	X	X
Color fundus photography	X	X	X	X	X

Abbreviations: BCVA, best-corrected visual acuity; EOS, End of Study; ETDRS, Early Treatment Diabetic Retinopathy Study; SD-OCT, spectral domain optical coherence tomography; SF-36v2, 36-item Short Form Health Survey; VFQ-25, Visual Function Questionnaire-25, version 2.

^a The inclusion window will be from Week 96 visit up to 1 day prior to Visit 2, which will be approximately 180 days post W96/EOS.

^b Subjects who discontinue participation in the long-term follow-up study prematurely (i.e., prior to Visit 5) will complete an EOS visit, including Visit 5 procedures.

- ^c Examination includes general appearance, skin, head, eyes, ears, nose, throat, neck, thyroid, chest/lungs, heart, abdomen, lymph nodes, extremities, and body weight and height. Vital signs include temperature, pulse rate, and systolic and diastolic blood pressure.

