3. STUDY DESIGN

3.1 OVERALL DESIGN

This study is a multinational, multicenter, prospective, non-interventional, long-term follow-up clinical study of subjects previously treated with GS010 in either the RESCUE or REVERSE studies. Of the 7 investigational centers participating, 4 are located in Europe (1 each in France, Germany, Italy, and the United Kingdom) and 3 are located in the United States.

Subjects were enrolled in the long-term follow-up study when informed consent was provided and inclusion/exclusion criteria are met. Enrollment occurred during the Inclusion Period, which was during the RESCUE and REVERSE study Week 96/End-of-Study (EOS) Visit or anytime up to 1 day prior to the long-term follow-up study Visit 2 (Day 180). Preferably, the assessments required to be performed during the Inclusion Period were conducted at the RESCUE and REVERSE study Week 96/EOS visit; however, if the subject could not undergo all assessments at that time, the assessments may have been performed at a later date during the Inclusion Period, but no later than one day before the Year 2.5 visit (Day 180 post Week 96 (Visit 12 of CLIN-03)).

[figure not shown]
The study population was limited to the number of subjects treated in the RESCUE or REVERSE studies. The total length of the long-term follow-up study is 3 years and the total length of the subject follow-up from IMP administration will be 5 years.

The follow-up includes onsite assessments of safety, QoL, and efficacy as performed in the RESCUE and REVERSE studies. The study includes 5 follow-up study visits: at 2, 2.5, 3, 4, and 5 years post-treatment.

Statistical analysis of the data will include descriptive summaries of safety, QoL assessments, and statistical testing of efficacy endpoints.

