Table 1: Schedule of Events

Years post-treatment Procedure	Inclusion Period	Long-term Follow-up Period			
	Year 2 (Week 96) ^a	Year 2.5 (± 4 weeks)	Year 3 (± 4 weeks)	Year 4 (± 4 weeks)	Year 5 EOS (± 4 weeks) ^b
Visit	Visit 1	Visit 2	Visit 3	Visit 4	Visit 5
Informed consent	X				
Clinical Assessments/Procedures					
Review inclusion/exclusion criteria	X				
Medical history	X				
Physical examination including vital signs ^c	X				X
Electrocardiogram (12-lead)	X				X
Review concomitant medications	X	X	X	X	X
Adverse events/serious adverse events ^d	X	X	X	X	X
Laboratory Assessments					
Hematology/serum chemistry including liver function ^e	X				X
Quality of Life Assessments					
VFQ-25 ^f	X		X	X	X
SF-36 ^f	X		X	X	X
Ocular and Vision Assessments					
Slit-lamp examination ^g	X	X	X	X	X
Goldmann applanation tonometry for intraocular pressure ^h	X	X	X	X	X
Refraction for BCVA	X	X	X	X	X
Visual Acuity (ETDRS)	X	X	X	X	X
Humphrey TM visual field 30-2	X	X	X	X	X
Pelli-Robson contrast sensitivity ^h	X		X	X	X
SD-OCT	X	X	X	X	X
Color fundus photography	X	X	X	X	X

Abbreviations: BCVA, best-corrected visual acuity; EOS, End of Study; ETDRS, Early Treatment Diabetic Retinopathy Study; SD-OCT, spectral domain optical coherence tomography; SF-36v2, 36-item Short Form Health Survey; VFQ-25, Visual Function Questionnaire-25, version 2.

^a The inclusion window will be from Week 96 visit up to 1 day prior to Visit 2, which will be approximately 180 days post W96/EOS.

^b Subjects who discontinue participation in the long-term follow-up study prematurely (i.e., prior to Visit 5) will complete an EOS visit, including Visit 5 procedures.

Sponsor: GenSight Biologics

Statistical Analysis Plan

Protocol No: GS-LHON-CLIN-06

Final Version 2.0 / 30-June-2022

- ^c Examination includes general appearance, skin, head, eyes, ears, nose, throat, neck, thyroid, chest/lungs, heart, abdomen, lymph nodes, extremities, and body weight and height. Vital signs include temperature, pulse rate, and systolic and diastolic blood pressure.
- ^d Record in the eCRF any AE that is causally related to study medication and/or study procedure, any ocular AE (causally related or unrelated to study medication and/or study procedure), and any SAE (causally related or unrelated to study medication and/or study procedure).

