8.4 TREATMENTS

8.4.1 Extent of Study Drug Exposure

This study is the follow up of RESCUE/REVERSE studies where a single IVT injection was administered into the randomized eye and a single sham IVT injection in fellow eye on same day. Therefore, no summary table will be produced for the exposure data.

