8.6.1 Adverse Events

All adverse events analyses will be presented with number of patients with at least one AE and number of events.

Primary Safety Analysis

The primary safety variables are:

- Adverse events (AEs) or serious adverse events (SAEs) (ocular or systemic) related to IMP (=GS010=study drug) or administration procedure, as judged by the Investigator, reported during the long-term follow-up visits (2, 2.5, 3, 4, and 5 years) from the period of 96 weeks up to 5 years post-treatment and summarized descriptively by type, frequency (number, percentage), severity, causal relationship, and seriousness.

Adverse events and SAEs related to study drug or study procedure will be summarized in two different ways: (1) systemic AEs and SAEs related to study drug or procedure or both, and (2) ocular AEs and SAEs related to study drug or procedure or both. Systemic AE data will be summarized by all subjects. Ocular AE data will be summarized by sham eye only, GS010 eye only, and both eyes.

The following summaries will be produced for (1) SAEs unrelated to study drug or procedure or both, (2) systemic AEs/SAEs related to study drug or procedure or both, and (3) ocular AEs/SAEs related to study drug or procedure or both, using counts and percentage as follows:

- Overall summary of AEs/SAEs related to study drug or procedure or both
- AEs related to study drug or procedure or both, including the number of events reported
- AEs/SAEs related to study drug or procedure or both by maximum severity
- AEs/SAEs related to study drug or procedure or both leading to study discontinuation
- SAEs related to study drug or procedure or both
- SAEs related to study drug or procedure or both leading to death.

Note that AE summaries will be provided for AEs collected during the originating study (RESCUE or REVERSE studies), for the follow-up period of CLIN-06, and combined.

Events will be coded using the current version of MedDRA and summarized by system organ class (SOC) and preferred term (PT).

Secondary Safety Analysis

The secondary safety endpoints are:

- Ocular or vision-related adverse events reported during the post-treatment long-term follow-up visits from the period of 96 weeks up to 5 years and summarized descriptively by type, frequency (number, percentage), severity, causal relationship, and seriousness.

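### SAP 8.6.1 reports the primary safety endpoint only as counts and percentages, with no follow-up time and no confidence interval

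*SAP*

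**What the plan says.** Protocol 7.2.1 and SAP 4.1 define the primary endpoint as ocular or systemic AEs and SAEs judged related to GS010 or its administration. The period, repeated in SAP 8.6.1, is "from the period of 96 weeks up to 5 years post-treatment".

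On presentation, SAP 8.6.1 states that "All adverse events analyses will be presented with number of patients with at least one AE and number of events", and its summaries use counts and percentages. A note in the same section adds that "AE summaries will be provided for AEs collected during the originating study (RESCUE or REVERSE studies), for the follow-up period of CLIN-06, and combined". Protocol 11.5.1 does not contain the parent-study and combined summaries, and SAP 8.8 does not list them as a change.

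SAP 8.6 places all safety analyses on the Safety Population. SAP 6.1 defines this as treated subjects who consented to the follow-up study, however long each was then observed. The intervals described in SAP 8 are for change scores and for the ANCOVA, GEE and logistic models; none is for AEs. SAP 8.1 counts withdrawals and visit attendance but does not summarise follow-up time.

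Observation differs between subjects. Consent may be given until the day before Visit 2 (Protocol 8.1), SAE reporting runs from consent to the end-of-study visit (Protocol 10.2), and subjects who leave are not replaced (Protocol 7.3.3).

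**The concern.** The study's main purpose is to detect delayed harm (Protocol 5.3). A percentage of a fixed population measures risk over the stated period only if everyone is observed for all of it. Subjects who leave early stay in the denominator, but their later events cannot enter the numerator. The reported percentage is then too low, and no table shows by how much.

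Once parent-period and follow-up summaries both exist, readers will compare them. The periods differ in length, so a difference in percentages does not indicate a difference in risk, and similar percentages do not indicate a stable one.

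Related SAEs years after a single injection may be few or absent. A bare zero in a small study invites the reading that there is no risk, when the data only exclude risks above some limit that the plan does not report.

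**Working it through.** The documents state no sample size, AE rate or dropout rate, so there is no planned figure to reproduce. Values marked *assumed* are illustrations.

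**Period lengths**
- Parent period: 96 weeks = 672/365.25 = 1.84 years.
- Follow-up: 5 × 365.25/7 − 96 = 260.9 − 96 = 164.9 weeks = 3.16 years.
- Ratio: 164.9/96 = 1.72.
- SAP 3.1 gives a rounder length: "The total length of the long-term follow-up study is 3 years". That is 156.5 weeks, ratio 1.63.
- The ±4-week window at Year 5 gives 160.9 to 168.9 weeks, ratio 1.68 to 1.76.
- Consent on Day 179 after Week 96 leaves 164.9 − 179/7 = 139.3 weeks, ratio 1.45.

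**Effect of length alone** (*assumed* constant rate of 5 per 100 subject-years; proportion with an event = 1 − exp(−rate × years))
- Parent period: 1 − exp(−0.05 × 1.84) = 8.8%.
- Follow-up: 1 − exp(−0.05 × 3.16) = 14.6%.
- Conversely, a rate that fell by 1 − 96/164.9 = 42% after Week 96 would give equal event counts, hiding a real decline.

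**Effect of dropout** (same rate; *assumed* 30% lost evenly over follow-up)
- Average proportion with an event before leaving, among those lost: 1 − (1 − exp(−0.158))/0.158 = 7.5%.
- Reported: 0.7 × 14.6% + 0.3 × 7.5% = 12.5%, against a true 14.6%.

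The next table takes a constant dropout rate μ with fraction d lost by Year 5, and an *assumed* event rate λ giving 10% in 96 weeks. The reported proportion is λ/(λ+μ) × [1 − exp(−(λ+μ)T)], with T = 164.9 weeks.

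| Lost by Year 5 | Reported in follow-up | Mean weeks observed | Event-count ratio to parent period |
|---|---|---|---|
| 0% | 16.6% | 164.9 | 1.72 |
| 10% | 15.7% | 156.5 | 1.63 |
| 20% | 14.9% | 147.8 | 1.54 |
| 30% | 14.0% | 138.7 | 1.44 |
| 50% | 12.1% | 118.9 | 1.24 |

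Length and dropout act in opposite directions. Event counts become equal only when about 70% are lost at a constant rate, or about 42% if all losses come at the start.

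**With person-time in the denominator**, a constant rate gives the same figure in both periods. In the table's example it is 5.7 first events per 100 subject-years in each, ratio 1.00, whatever the dropout, provided dropout is unrelated to AE risk.

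**Bound for zero events** (exact two-sided 95% upper limit = 1 − 0.025^(1/N))
- *Assumed* N = 40: 8.8%. N = 60: 6.0%. N = 80: 4.5%.
- As a rate, for N = 60 all followed for 3.16 years: −ln(0.025)/(60 × 3.16) = 3.689/189.6 = 1.95 per 100 subject-years.

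**The case against.** The strongest reply is that the plan is descriptive by design. Protocol 11.3 rules out inferential statistics on the primary endpoint, SAP 8.1 shows withdrawals and missed visits, SAP 8.6.1 lists all recorded AEs, and a reader can compute exact limits from n and N. This is partly right: dropout is not invisible, and no hypothesis test is missing. But the disposition table is not tied to the AE percentages, and rates and intervals can be descriptive without contradicting Protocol 11.3.

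A second reply stands in full for what it covers. Each subject has one GS010 eye and one sham eye with the same follow-up, so the ocular AE contrast within a period is not biased by period length. Systemic AEs have no such control, and absolute percentages and comparisons between periods remain affected.

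Several stronger readings are tempting, but the documents do not support them:

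- *That the tables will show rising late risk.* This needs a constant hazard and equal capture. In Protocol 10.1.2 the possible, probable and related categories all require a reasonable time relation to administration, so a constant hazard over five years is doubtful for related events. If CLIN-06 captured about 58% (96/164.9) of events or fewer, the rise would vanish. The SAP plans no test between periods and does not say that the summaries share a table.
- *That the primary endpoint spans all three summaries.* It covers Week 96 to Year 5 only; the other summaries are additions.
- *That SAP 8.4.1 removes follow-up time.* The sentence "Therefore, no summary table will be produced for the exposure data" concerns drug exposure, which is one injection and one sham for everyone. It is reasonable as it stands.
- *That the AE classes differ between periods.* The follow-up instruction, "Record in the eCRF any AE that is causally related to study medication and/or study procedure, any ocular AE" and any SAE, does limit collection. The main summaries in SAP 8.6.1 are already confined to related, ocular and serious events, and the documents do not describe collection in the parent trials.

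**Conclusion.** The point holds as a reporting gap in the primary safety result. With no follow-up time, the Week 96 to Year 5 percentage is lowered by dropout. Late consent lowers it too, to the extent that events before consent are not recovered at Visit 1. For 10% to 50% lost, the table's true 16.6% would appear as 15.7% to 12.1%. Percentages from the 96-week and 165-week periods cannot be read against each other; the constant-hazard ratio is 1.72, or 1.45 to 1.76 across the readings of follow-up length above. Zero events has no stated bound, although the upper limit would be 8.8% to 4.5% for 40 to 80 subjects.

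The period lengths, the count-and-percentage presentation and the absence of rates and intervals in SAP 8 and 8.6 come from the documents. The hazard, the dropout and N are assumptions. That the percentages use the whole Safety Population as denominator is the natural reading of SAP 8.6, though no denominator rule is spelled out. A reader might infer that the plan will produce a false signal of late harm. The documents do not establish that direction, only that the planned figures cannot separate risk from time observed.

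**What to change.** In SAP 8.6.1:

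1. Add a table of observed follow-up time in CLIN-06, counted from Week 96, or from consent where AE/SAE reporting began later, to last contact. Starting everyone at Week 96 would count time for late consenters before CLIN-06 reporting began and could dilute the rates.
2. For the AE classes already summarised, add incidence per 100 subject-years (eye-years for ocular AEs) with exact Poisson 95% intervals, separately for injection to Week 96 and for the CLIN-06 period.
3. Add exact binomial 95% intervals to the primary-endpoint percentages.
4. Label all of these descriptive.

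The sentence in SAP 8.4.1 and the AE classes can stay as they are.

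The inputs are treatment, consent, visit, withdrawal and AE onset dates already collected, so study conduct does not change. The cost is a few more table columns and a slightly less favourable safety statement, because upper limits are shown.

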8.6.2 Laboratory Data

Parameters analyzed by the central laboratory will be used for statistical analysis. The laboratory test includes the following:

- Hematology tests and other blood laboratory tests: Complete blood count including red blood cells, hemoglobin, hematocrit, white blood cells with differential counts and platelets.
- Blood chemistry tests: Glucose, lipase, amylase, calcium, sodium, potassium, chloride, bicarbonate, blood urea nitrogen (BUN) and creatinine.
- Liver function tests: AST, ALT, ALP, γ GT, total bilirubin and albumin

The statistical analysis of clinical laboratory tests will be conducted as described below.

Descriptive analysis (number of subjects, mean, SD, median, Q1, Q3, minimum, maximum) of each parameter at each time point and the changes from baseline;

Individual data listings of laboratory results will be presented for each subject at all study visits (scheduled and non-scheduled), including normal range limits for each laboratory test.

Out-of-range results will be flagged, and determinations of whether the results were considered to be of clinical significance by the investigator will be included. Clinically significant abnormal lab values for different parameters will be summarized at each post baseline time point.

Additionally, a summary will be presented of subjects who had an out-of-range result, including the subject, visit date, baseline value, normal range and out-of-range value observed.

8.6.3 Vital Signs

Systolic and diastolic blood pressure, pulse rate and body temperature will be displayed in summary tables including number of subjects, mean, SD, median, Q1, Q3, minimum and maximum by Visit. The descriptive statistics for change from baseline will be presented in the same way.

Individual data listings of systolic and diastolic blood pressure, pulse rate and body temperature will be produced for all subjects over time.

8.6.4 Physical Examinations, ECGs, and Other Observations Related to Safety

8.6.4.1 Physical Examination

All physical examination data will be listed by subject. No summary tables or analysis will be produced.

8.6.4.2 Electrocardiogram

The number and percentage of subjects with normal, abnormal clinically significant and abnormal but not clinically significant ECG findings will be summarized by Visit.

All ECG data will be listed by subject.

8.7 EXPLORATORY ANALYSES

8.7.1 Exploratory efficacy analyses

As an exploratory analysis, the response to treatment through Visit 5 (Year 5) using a MMRM model will be performed. The change from baseline in the LogMAR will be the response. Change from baseline of all-GS010 eyes will be compared to the change from baseline of all-sham eyes. The model will include subject as a random factor and fixed effects for treatment, follow-up visit (time point), eye status at baseline (better or worse), time from onset of disease and LogMAR at baseline as a covariate. The following interactions will be explored: baseline LogMAR and treatment; time from onset of disease and treatment; and eye status at baseline and treatment. The estimate of treatment effect at various follow-up time points and its 95% confidence interval (CI) will be presented. A UN@AR(1) (Autoregressive(1)) covariance structure will be fit to accommodate the doubly repeated measures data (repeated over time and eye). In the event of convergence problems with this covariance structure, other covariance structures will be explored.

Time course analysis of log of contrast sensitivity (LogCS), Humphrey visual field parameters and SD-OCT parameters will be conducted similarly to the time course analysis of LogMAR.

Other exploratory analyses will be performed for all analysed visits as a sensitivity analysis, excluding off-chart evaluations whose distance to the subject was superior to 2 meters. The endpoints analysed will be the ones described in 8.5.2.2 at eye level.

Additional exploratory analyses may be performed in the study.

